Our long-term goal is the reduction of morbidity associated with cannabis and smoking through the implementation of cost-effective, evidence-based interventions that maximize recovery. The purpose of this **pilot** project is to evaluate feasibility of treatment, recruitment, and abstinence bioverification methods for a combined cannabis and tobacco smoking tele-health mCM intervention that will effectively treat both disorders. Results from this pilot project will be used in support of an NIH grant to further develop the treatment and evaluate its feasibility and acceptability on a larger scale.

Preliminary Data

We developed and tested the mCM smoking app in combination with telephone CBT and used them in an initial validation study of 22 smokers with posttraumatic stress disorder (PTSD; Hertzberg et al., 2013). In this study, participants were randomized to 4 weeks of mCM plus CBT or to CBT plus yoked non-contingent reinforcement condition (i.e., compensation was based on earnings of participant matched from the other condition). Participant adherence to the protocol of submitting two on-time valid video readings daily was excellent (92%). Three-month self-reported 7-day point-prevalence quit rates were 18% in the yoked group and 50% in the mCM group. These preliminary results suggest that the tele-health mCM intervention is feasible and may lead to a longer duration of abstinence when CBT complements mCM in a multi-component intervention.

To further evaluate the tele-health mCM intervention, we enrolled 20 homeless smokers, and they all received the tele-health mCM intervention with CBT and standard smoking pharmacotherapy (Carpenter et al., 2015; Hertzberg et al., 2013). The majority of the sample (70%) had a history of CUD. Adherence to the timing and procedures for uploading videos with the mCM app was excellent during the treatment phase (93%). After 4 weeks of the tele-health mCM intervention, bioverified 7-day point-prevalence abstinence was 50%. Despite removing monetary compensation for abstinence at 4 weeks post-quit, bioverified abstinence in the tele-health mCM group was 55% at a 3-month follow-up assessment, and 45% at a 6-month follow-up assessment (Carpenter et al., 2015).

Methods

Participants

Up to 10 participants with CUD and smoking will be enrolled, with a goal of 5 participants completing the intervention.

Participants will be eligible for inclusion in the study if they meet the following criteria:

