- 1. The Fagerström Test of Nicotine Dependence (FTND; Heatherton, Kozlowski, Frecker, & Fagerström, 1991) with additional smoking history questions (e.g., number of cigarettes smoked/day, age of first smoking, number of previous quit attempts);
- 2. Marijuana Smoking History (Bonn-Miller & Zvolensky, 2005);
- 3. Motives for Marijuana Use (Simons, Correia, Carey, & Borsari, 1998);
- 4. Posttraumatic Stress Disorder Checklist (PCL5; Weathers, Litz et al., 2013);
- 5. Traumatic Life Events Questionnaire (TLEQ), which collects the occurrence and frequency of each of 22 traumatic events (Kubany et al., 2000);
- 6. Patient Health Questionnaire (PHQ-9; Kroenke, Spitzer, & Williams, 2001);
- 7. Beck Depression Inventory (BDI; Beck, Steer, & Brown, 1996);
- 8. Beck Scale for Suicidal Ideation (BSS; Beck & Steer, 1991);
- 9. Conners' Adult ADHD Rating Scale (CAARS; Conners, Erhardt, & Sparrow, 1998);
- 10. Cannabis/Tobacco Version of the Stroop Test, computerized (Streeter et al., 2008);
- 11. Delay Discounting Task, computerized (Richards et al., 1999);
- 12. Iowa Gambling Task, computerized (Bechara et al., 1994); and
- 13. Balloon Analogue Risk Task, computerized (Lejuez et al., 2002).

Computerized Tasks. Several computerized measures will be given in order to measure impulsivity. Measures will be purchased as a package from www.millisecond.com. Computerized measures will be given on a Duke-owned laptop that is not connected to the internet. Results will be stored temporarily on the hard drive of that computer. Data will be moved from the laptop to the Duke server (duhsnas-pri\dusom_psych\private\[name] Logs\Marijuana and Smoking) via encrypted thumbdrive or encrypted DVD. Once data are moved to the Duke server, they will be deleted from the hard drive of the laptop.

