Pharmacotherapy for Smoking Cessation. Participants will receive standard pharmacotherapy for smoking cessation. Study medications will be mailed to participants after the screening visit. Study medications consist of bupropion, an 8-week course of nicotine patch use and up to two rescue methods (e.g., nicotine gum, lozenge). Participants will be screened for suitability for nicotine replacement therapy (NRT) or other smoking cessation medication, and the study physician will determine safety for NRT and bupropion use. Participants will receive tailored amount and delivery type of NRT based on number of cigarettes smoked per day using an established protocol (Bars et al., 2006). Bupropion will be prescribed to start one week prior to their quit day [150 mg/daily for days 1-7 and 300 mg/daily (administered in two daily doses) until the 6-month follow-up. If a participant with a seizure disorder, history of or current hepatitis and/or cirrhosis, renal impairment, and/or uncontrolled diabetes wishes to enroll in the study, he/she will not receive contraindicated medications. If a participant with any of these medical conditions is unwilling to participate in the study without taking bupropion, he/she will be withdrawn from the study.

Follow-Up Visits. Participants will be asked to attend three follow-up visits at end of treatment, 3- and 6-months post-quit. At the follow-up visits, participants will be asked about their experiences with various treatment components. These will include closed ended questions and open-ended interview

questions. In addition, the study coordinator will ask questions about alliance with the study therapist. Participants will be asked to complete symptom self-report measures and computerized impulsivity tasks at each follow-up visit. Participants will be asked about smoking and cannabis use in the period since the quit date. Self-reported abstinence will be bioverified by several means. Self-reported prolonged abstinence from cannabis use will be verified by urine and OF cannabis assessments. Self-reported abstinence from smoking will be verified by saliva cotinine assay and CO reading.

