Participants will be offered NRT, and there are risks associated with the use of NRT. Minimal risks associated with wearing a nicotine patch include skin irritation, dizziness, lightheadedness, increased heart rate or blood pressure, nausea or vomiting. If a participant indicates a contraindication to NRT (e.g. uncontrolled hypertension), medical clearance for NRT will be sought from the participant's primary care physician and/or the study physician. If a participant with a seizure disorder, history of or current hepatitis and/or cirrhosis, renal impairment, and/or uncontrolled diabetes wishes to enroll in the study, he/she will not receive contraindicated medications.

Participants who are medically eligible will also be prescribed bupropion SR. Risks of bupropion use include dry mouth, insomnia, nausea, constipation, headache, shakiness or jitteriness, skin rash, sweating, allergic reaction, change in appetite, weight loss, dizziness, tremor, thinking abnormally, hot flashes, worsening depression or suicidal thoughts and behavior, and ringing in the ears. At the highest dosage of bupropion to be used in this study, seizures occurred in 1 out of every 1000 (0.1%) who took this drug. Participants are informed that they are not required to take bupropion, and will be allowed to participate in the study if they refuse to do so.

There is a potential risk associated with the loss of confidentiality of study data. Specifically, collection and transfer of videotaped carbon-monoxide monitoring have risks with regards to privacy and confidentiality. Please see "Protection From Risk: Data Security" for details on reduction of risk with regards to the proposed videotaping.

Protection From Risk: Data Security

While participants may benefit from quitting smoking and marijuana use, there are no guaranteed benefits to the individual participant and no immediate benefits of the proposed research to others. There are potential benefits to others from the information generated that potentially will be helpful in developing new combined treatments for smoking and marijuana use. In our opinion, the anticipated benefits of this study outweigh the potential risks. The study is completely voluntary and participants are informed that they are free to refuse to answer any items on the questionnaires or questions from the interview. They are also informed that they are free to decline participation in procedures and can withdraw from the study at any time.

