semi-parametric methods (e.g. quasi-likelihood methods; McCullagh & Nelder, 1989). In planning a full RCT of the tele-health mCM intervention for CUD and smoking, it is important to evaluate study feasibility and treatment procedures, as well as gaining information about effects on proposed outcome variables. To remain consistent with guidelines for designing and evaluating pilot studies, analyses will be primarily descriptive (Thabane et al., 2010) and aimed at informing feasibility and needed modifications rather than detecting statistically significant between-group differences (Leon, Davis, & Kraemer, 2011). However, to best utilize participant data to optimally design the treatment, we have established several objectives to indicate whether the planned trial is feasible.

Feasibility of cannabis abstinence assessment will be based on data from this pilot. While the validity of the Alere Oratect Oral Fluid Drug Screen Device has demonstrated excellent agreement with clinical samples analyzed with GC/MS methods, the utility of using daily saliva tests and CO (which measures carbon monoxide for cannabis smoking in the past 3 hours) has not been evaluated. We will examine the utility of the proposed saliva testing protocol. Additionally, qualitative data on the use of saliva tests will be examined to ensure that participants find it acceptable and preferable to in-clinic assessment methods.

The feasibility and acceptability of the multi-component tele-health mCM intervention will be assessed. We will collect frequency data regarding the number of videos transmitted, number of study measures completed at each time point, the amount of missing data (including missed videos), the number of sessions attended, and the frequency and severity of adverse events. We will assess the association of potential stratification variables (sociodemographic, psychiatric, and CUD/smoking severity variables) with feasibility indices, adherence to study protocol (video transmission, completion of study measures at each time point, session attendance), attrition, and adverse events. We will also determine whether attrition rates and frequency and severity of adverse events exceed those of previous smoking treatment trials. These data will provide important information useful in refining the intervention and associated assessments/procedures prior to their implementation in a larger-scale RCT.

References

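### The safety analysis rests on adverse events alone, so worsening on the depression and suicidal-ideation scales can be missing from it and is not shown as within-person change

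*Combined protocol and SAP*

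**What the plan says.** - **Named harm.** Potential Risks includes, among bupropion effects, "worsening depression or suicidal thoughts and behavior, and ringing in the ears". The same section lists depressed and anxious mood among the effects of quitting cannabis and of quitting smoking. Bupropion is optional: "Participants are informed that they are not required to take bupropion". Under Pharmacotherapy for Smoking Cessation it runs from one week before quit day to the 6-month visit.
- **Instruments.** The Measures list, introduced as part of screening, contains the PHQ-9, BDI and BSS. Follow-Up Visits states: "Participants will be asked to complete symptom self-report measures and computerized impulsivity tasks at each follow-up visit". Table 1 shows questionnaires at sessions 7, 8 and 9.
- **Adverse-event capture.** The Data and Safety Monitoring Plan gives staff contact, a toll-free line and weekly meetings as the routes. The PI rates severity and attribution, and the study physician reviews event reports. Protection From Risk: Data Security promises close watch on symptoms. A separate section on suicidal ideation describes a risk policy with escalation when an interview finds moderate or high risk.
- **Analysis.** Data Analyses, in both copies, lists "the number of sessions attended, and the frequency and severity of adverse events", and compares adverse events with earlier smoking trials. Psychiatric variables have one specific role: "We will assess the association of potential stratification variables (sociodemographic, psychiatric, and CUD/smoking severity variables) with feasibility indices", and likewise with adherence, attrition and adverse events. Otherwise they fall under the general rule for continuous variables, which gives group summaries and plots.
- **Size.** "Up to 10 participants with CUD and smoking will be enrolled, with a goal of 5 participants completing the intervention".

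**The concern.** The trial names a harm, owns instruments that measure it, and appears to repeat them while the drug may still be taken. The analysis plan does not use them as safety data. Psychiatric variables enter as possible predictors of adverse events, and the safety outcome is the adverse-event record alone. A participant whose score rises on treatment, and whose worsening is not logged by another route, would not be in that result. The group summaries do not recover the information, because they do not say whether a high follow-up score is new. The adverse-event frequency is to be compared with earlier smoking trials and carried into planning a larger RCT. Any loss of such cases would push that comparison in the favourable direction.

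**Working it through.** The plan states no figure on this point, so there is none to reproduce. The check is a trace through the text, followed by illustrations. **Every score below is assumed; the documents give none.**

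**1. Trace from scale to safety result.**
- Collection: screening names the three scales; follow-up names only their class.
- Score to event: no cut-off, change or review step is stated. The grading scales mentioned in the monitoring plan rate an event already recorded.
- Event to analysis: frequency and severity only.
- Score to analysis: box plots, histograms, means with SDs, ranges and percentiles. No paired change is specified.

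**2. Timing.** Session 7 falls 2 + 2 + 2 = 6 weeks after quit day, so about 6 + 1 = 7 weeks after bupropion starts. Table 1 shows no scheduled contact between session 7 and the 3-month visit, or between the 3- and 6-month visits. The follow-up questionnaires are then the only scheduled mood measure the documents state.

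**3. Can group summaries hide one worsening?**
- Five completers, four falling 5 points and one rising 10: mean change = (4 × (−5) + 10)/5 = −2.0, with 1 of 5 (20%) worse. For the same five people, the difference between visit means is the same −2.0.
- One person rising 20 and each of the others falling 3: mean change is (20 − 12)/5 = +1.6 with n = 5, and (20 − 27)/10 = −0.7 with n = 10; the median change is −3 in both. With falls of 0 to 5 in the others, the mean change runs from +4.0 to 0.0 (n = 5) and from +2.0 to −2.5 (n = 10). The mean does not always hide the case.
- Ranges and plots. Take ten people in the same order at both visits. Screening: 8, 10, 12, 12, 14, 15, 16, 18, 22, 30. Follow-up: 28, 8, 9, 10, 11, 12, 13, 14, 17, 20. Means are 157/10 = 15.7 and 142/10 = 14.2; ranges are 8–30 and 8–28. With interpolated quartiles, the upper box-plot fences are 17.5 + 1.5 × 5.5 = 25.75 and 16.25 + 1.5 × 6 = 25.25. Each visit therefore shows one high outlier (30, then 28). They are different people, and the first participant has risen by 20. Only pairing shows this.

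**4. Attrition, if visit means use everyone available.** The plan does not say which participants enter each visit's summary. Suppose 10 are screened and 5 return, non-completers average 14, and completers average 8 with no change. The screening mean is (5 × 14 + 5 × 8)/10 = 11 against 8 later, an apparent gain of 3 = 0.5 × (14 − 8). Baseline gaps of 2 to 8 give 1 to 4 points.

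**5. Weight of one case.** Zero recorded events are compatible, at a one-sided 95% level, with a true rate of up to 1 − 0.05^(1/n): 45% for n = 5 and 26% for n = 10. At assumed true rates of 5%, 10% and 20%, the chance of at least one case, 1 − (1 − p)^n, is 23%, 41% and 67% (n = 5) or 40%, 65% and 89% (n = 10). One uncaptured case can turn a finding of some events into none.

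**The case against.** The best defence is that this is a single-arm, descriptive feasibility pilot with no safety hypothesis, that worsening has other ways into the record, and that with 5 to 10 people an extreme score may be noticed without a special rule.

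Much of that stands. Symptom monitoring, weekly review by the PI, a psychiatrist as study physician and the suicide-risk policy are real safeguards. The full emergency procedure and risk standards are not reproduced, so the missing link from score to event can be asserted only of the text available. Box plots and histograms are planned and may reveal an outlier. Table 1 allows 30 minutes at each of sessions 8 and 9 against 3½ hours for screening, so a shortened follow-up battery is possible. The scales also add nothing before session 7, when phone contacts are the route.

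Three stronger readings are tempting and not supported:
- *All three scales are known to be repeated at every lab visit.* No follow-up text names them.
- *Worsening will be absent from the adverse-event result, or the trial lacks a response to suicidality.* The routes above rule this out; only that it can be missing is supported.
- *The scales are left unanalysed.* All study variables are to be summarised.

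What the defence does not supply is paired change. An outlier on a plot does not say whether the score is new, and a descriptive aim does not exclude a descriptive listing.

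**Conclusion.** The point holds as a minor improvement. The stated safety analysis does not use the mood and ideation scales, and the stated summaries cannot separate emergent worsening from a high screening score. No bias can be quantified, since the illustrations show only what is possible. The conclusion rests on two assumptions: that at least some of the three scales are among the repeated measures, and that no unseen procedure already feeds scores into the adverse-event record. It is a gap in analysis and ascertainment, and implies nothing about the adequacy of clinical care.

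**What to change.** In Data Analyses:
1. State which of PHQ-9, BDI and BSS are given at sessions 7, 8 and 9.
2. List each participant's paired change from screening at those visits, marked by bupropion use.
3. Beside the adverse-event frequency, report the number who worsened on each scale, using analysis cut-offs that the study team fixes before analysis. The choice of cut-off, and any clinical action, is theirs.
4. Report separately the screening scores and last available status of participants without follow-up, so that the paired summary is not read as covering people who left.
5. State that the listing is descriptive and that, with no control arm, it cannot separate bupropion effects from withdrawal effects.

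Cost: a few lines of text and one listing of at most 10 × 3 = 30 rows per scale (5 × 3 = 15 with five completers). If the scales are already repeated, no new data are needed. The downside is a possibly less favourable safety picture.

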 Randomized controlled trial of motivational enhancement therapy with nontreatment-seeking adolescent cannabis users: A further test of the teen marijuana check-up. *Psychology of Addictive Behaviors*, 25, 474-84. PMCID: PMC3177997.
- Zhang, Y. & Wildermuth, B.M. Qualitative analysis of content. In: Wildemuth, B., ed. *Applications of social research methods to questions in information and library science*. Westport, CT: Libraries Unlimited; 2009:308-19.

Data Analyses

Descriptive statistics will be used to summarize all study variables. For continuous variables, means, standard deviations, percentiles, ranges, box plots and histograms will be generated. For categorical variables, frequencies and proportions will be generated. We will examine all variables to determine if parametric distributional assumptions (e.g. normality for the continuous variables) are valid. Variables not meeting distributional assumptions will either be transformed or modeled using nonparametric or semi-parametric methods (e.g. quasi-likelihood methods; McCullagh & Nelder, 1989). In planning a full RCT of the tele-health mCM intervention for CUD and smoking, it is important to evaluate study feasibility and treatment procedures, as well as gaining information about effects on proposed outcome variables. To remain consistent with guidelines for designing and evaluating pilot studies, analyses will be primarily descriptive (Thabane et al., 2010) and aimed at informing feasibility and needed modifications rather than detecting statistically significant between-group differences (Leon, Davis, & Kraemer, 2011). However, to best utilize participant data to optimally design the treatment, we have established several objectives to indicate whether the planned trial is feasible.

Feasibility of cannabis abstinence assessment will be based on data from this pilot. While the validity of the Alere Oratect Oral Fluid Drug Screen Device has demonstrated excellent agreement with clinical samples analyzed with GC/MS methods, the utility of using daily saliva tests and CO (which measures carbon monoxide for cannabis smoking in the past 3 hours) has not been evaluated. We will examine the utility of the proposed saliva testing protocol. Additionally, qualitative data on the use of saliva tests will be examined to ensure that participants find it acceptable and preferable to in-clinic assessment methods.

The feasibility and acceptability of the multi-component tele-health mCM intervention will be assessed. We will collect frequency data regarding the number of videos transmitted, number of study measures completed at each time point, the amount of missing data (including missed videos), the number of sessions attended, and the frequency and severity of adverse events. We will assess the association of potential stratification variables (sociodemographic, psychiatric, and CUD/smoking severity variables) with feasibility indices, adherence to study protocol (video transmission, completion of study measures at each time point, session attendance), attrition, and adverse events. We will also determine whether attrition rates and frequency and severity of adverse events exceed those of previous smoking treatment trials. These data will provide important information useful in refining the intervention and associated assessments/procedures prior to their implementation in a larger-scale RCT.
